### 7.8.2 Primary Objective: Calculation of Epidemiological Measures of Interest

Descriptive statistics will be calculated for the cases and controls in terms of age of child at diagnosis, age of mother at the time of delivery, mode of delivery, maternal genital warts history, maternal smoking status, education level (mother), family income, and mother's

PRODUCT: V501/V503	PROTOCOL/AMENDMENT VERSION NO.: V503-095-00-v3
REVOPS ID NO: NIS102781	CORE DRC APPROVAL DATE: 18MAR2024
EPIDEMIOLOGY NO.(PE STUDIES ONLY): 08039.022	

country of birth using t-test or chi-2-test for differences in continuous and categorical variables, as appropriate. Conditional logistic regression will be conducted for estimation of ORs and corresponding 95% confidence intervals, with adjustment for relevant covariates. For a detailed discussion of covariates of interest, please see Annex 1, which lists subject matter expertise analysis of the association of interest, and potential confounding thereto. Annex 1 also motivates closely the inclusion of covariates described here below.

In case-control studies, it is actually the odds of exposure which is typically assessed among cases of a disease and then compared with odds of exposure among controls. However, the odds ratio is the same regardless of how it is defined in terms of marginal probabilities, i.e., probability of exposure given disease or probability of disease given exposure are statistically and technically equivalent. As per standard practice, it was therefore chosen to express ORs as the probability of disease given exposure, to provide a measure of the association between vaccine receipt and disease outcome.

Potential confounders such as mode of delivery, as well highest level of family income and education achieved by the mother (tentatively in tertiles relative to the general age-matched population in each of the respective countries) will be adjusted for when investigating the primary objective, through inclusion in the conditional logistic regression. Sensitivity analyses will be conducted in relation to the primary objective to assess the impact of: vaccine exposure definition (fully vaccinated versus  $\geq 1$  vaccine dose), age at vaccination ( $< 17$  years versus  $\geq 17$  years), outcome definition (ICD-10 code D14.1 versus cases [of D14.1] that have at least one associated treatment/procedural code and/or specified with subcode D14.1.A/“larynx papilloma”), time since vaccination ( $\leq 10$  years versus  $> 10$  years), and maternal history of EGW prior to delivery (yes versus no). To assess if older vaccinated women are a higher risk group, history of genital warts will also be presented separately among vaccinated women (i.e., history of genital warts prior to vaccination), stratified according to attained age at time of vaccination and compared with history of genital warts among unvaccinated women with same attained age. In the analysis, the group of women with history of genital warts prior to vaccination will be considered separately, if appropriate, i.e., assuming history of genital warts is not strongly associated with HPV vaccine uptake. If vaccination is found to be effective in preventing JoRRP among children whose mother had history of EGWs prior to delivery then it would suggest that vaccination not only prevents acquisition of infection in the mother but also prevents transfer of infection from infected mother to child, e.g., through maternal transfer of antibodies or other mechanism. OR estimates from the regression model will be inspected in terms of point estimates and precision, for comparison with results from the main analysis. Effect size (OR) estimates are expected to vary across most sensitivity analyses. For example, effectiveness may be higher among females that are fully vaccinated, vaccinated at younger age (prior to sexual debut), and without history of EGW.

There will be no adjustment for multiple comparisons in this study. Analyses have been pre-specified, discriminating between primary and sensitivity analyses, and all results will be reported.

PRODUCT: V501/V503	PROTOCOL/AMENDMENT VERSION NO.: V503-095-00-v3
REVOPS ID NO: NIS102781	CORE DRC APPROVAL DATE: 18MAR2024
EPIDEMIOLOGY NO.(PE STUDIES ONLY): 08039.022	

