### 7.2.3 Stratification

Stratified analyses, statistical adjustment, and/or assessment of interaction will be performed for the primary objective according to the following factors:

- 1) Age at vaccination of mother (before 17 years of age vs 17 years or older)
- 2) Time since vaccination of mother ( $\leq 10$  years vs  $> 10$  years)
- 3) Maternal history of external genital warts prior to delivery (yes/no)

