#### Conclusions on potential confounders:

**Socioeconomic status** (income/education) appears to be moderately-strongly associated with exposure; however, there have been no studies conducted in the Nordic region assessing association with outcome of JoRRP. Studies conducted in other regions (Canada and the U.S.) support an association and it is likely that an association also exists in the Nordic region. Country of birth has been found to be strongly associated with HPV vaccine uptake in Denmark but an association with JoRRP has not been assessed. In the interest of obtaining the best evidence, this association and association between socioeconomic status and JoRRP should be evaluated formally. It is therefore planned to include these factors as potential confounders in the analysis.

Regarding **sexual behavior**, the association with HPV vaccine exposure appears to be weak, whereas that with AoRRP (proxy for JoRRP) is stronger. In Sweden, riskier sexual behavior was positively associated with willingness to be vaccinated, and therefore bias (due to this confounder) may be expected to be towards the null. Although number of sexual partners cannot explicitly be adjusted for in the proposed register-based study, the analysis will include adjustment for income, education and smoking as a proxy for sexual behavior. Additionally, analyses will be performed separately considering history of genital warts prior to vaccination. Stratified analyses will also be conducted by age at vaccination, as minimal bias due to sexual behavior would be expected among those vaccinated at younger ages.

PRODUCT: V501/V503	PROTOCOL/AMENDMENT VERSION NO.: V503-095-00-v3
REVOPS ID NO: NIS102781 EPIDEMIOLOGY NO.(PE STUDIES ONLY): 08039.022	CORE DRC APPROVAL DATE: 18MAR2024

While at least some association between **method of delivery** and JoRRP appears likely, it is unknown if any association exists with vaccine uptake. This variable will therefore be explored as a potential confounder in the analysis.

Considering that **maternal history of external genital warts** is so strongly associated with outcome of JoRRP and likely lies on the causal pathway (i.e., maternal acquisition of HPV types 6/11, progression to EGW, and transmission of causal HPV infection to child during delivery), it may not be appropriate to adjust for this variable in evaluation of vaccine effectiveness. Stratified analyses will be performed according to maternal history of EGW prior to delivery (yes/no).

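### An effect among mothers with genital warts before delivery cannot show that vaccination blocks mother-to-child transfer, because that stratum is itself shaped by vaccination

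*Protocol*

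**What the plan says.** Protocol sections 7.2.3 and 7.8.2, the Annex 1 conclusions on confounders and Annex 2 Table 3 note 2(c) all plan a split by maternal EGW history, yes or no, with delivery as the cut-off date. In 7.8.2 it is one of a list introduced by "Sensitivity analyses will be conducted in relation to the primary objective to assess the impact of".

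Annex 1 explains why EGW is not an adjustment factor: it "is so strongly associated with outcome of JoRRP and likely lies on the causal pathway", so "it may not be appropriate to adjust for this variable in evaluation of vaccine effectiveness". The next sentence plans the stratification all the same.

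Section 7.8.2 then fixes how one result is to be read. Should the EGW-yes stratum show protection, the protocol takes this, in tentative terms, as a sign of two separate actions: "vaccination not only prevents acquisition of infection in the mother but also prevents transfer of infection from infected mother to child". It gives maternal antibodies as one possible route. It also says that effectiveness may be higher in women without EGW history.

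Related provisions:
- Section 7.8.1 and Table 3 footnote 4 remove mothers with warts before vaccination from the primary comparison.
- Section 7.8.2 compares pre-vaccination wart history with unvaccinated women of the same attained age, and treats the pre-vaccination-warts group separately if appropriate.
- Table 3 note 2(d) adds a table that ignores EGW history.

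**The concern.** A wart recorded before delivery may have come before or after vaccination. If after, it is an event that vaccination makes less likely. Splitting on such a variable conditions on a consequence of exposure, just as adjusting for it would, and Annex 1 already doubts that adjusting is appropriate.

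The transfer reading needs vaccinated and unvaccinated mothers in the EGW-yes stratum to be equally likely to carry transmissible HPV 6/11 at delivery. Nothing in the design secures this. The vaccine selectively removes 6/11 warts, and section 5 attributes more than 90% of RRP to those types. A history of warts is also not the same as a 6/11 infection at delivery, so a new infection prevented in the mother could produce the same result.

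At stake is a mechanistic statement about protection of the child despite maternal infection. The protocol provides for it in advance and does not name the competing explanations.

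**Working it through.** The plan gives no figure for this inference, so there is none to reproduce. The check sets the effect on transfer to zero and asks what the EGW-yes stratum would show.

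**Inputs**
- ve, effectiveness against 6/11 warts: 38% to 88%, from the prior Nordic registry studies in section 7.5. Those figures are for all genital warts. If the vaccine acts only on 6/11 warts, the type-specific value is at least as high, so using them directly does not inflate the result.
- s, the share of warts in unvaccinated mothers due to 6/11: not in the documents. Assumed 0.90, range 0.70 to 0.95.
- JoRRP risk from non-6/11 warts: assumed zero, in line with the more than 90% attribution in section 5. Also tried at 0.1 of the 6/11 risk.

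**1. Type mix (warts after vaccination)**

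Share of 6/11 among vaccinated mothers with warts = s(1−ve) / [s(1−ve) + 1−s]. Among unvaccinated mothers it is s. The stratum OR, unvaccinated versus vaccinated as in Table 3, is the ratio of the two: OR = (1 − s·ve)/(1 − ve).

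With s = 0.90:
- ve = 0.38: (1 − 0.342)/0.62 = 1.06
- ve = 0.60: (1 − 0.540)/0.40 = 1.15
- ve = 0.88: (1 − 0.792)/0.12 = 1.73

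The corresponding apparent effectiveness is 6%, 13% and 42%. Over the whole range of s and ve, the OR runs from 1.03 (s = 0.95, ve = 0.38) to 3.20 (s = 0.70, ve = 0.88). Giving non-6/11 warts 0.1 of the 6/11 risk changes the s = 0.90 results only to 1.05 to 1.60.

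**2. Prevented new infection (if mothers with pre-vaccination warts stay in the table)**

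Let a be the chance that the old infection persists to delivery and b the chance of a new 6/11 infection before delivery. Both are assumed, at 0.05 to 0.20. The vaccine prevents only new infection, with ve 0.6 or 0.9.

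Unvaccinated: 1 − (1−a)(1−b). Vaccinated: 1 − (1−a)(1−b(1−ve)).

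With a = b = 0.10 and ve = 0.6: 1 − 0.9×0.9 = 0.190 against 1 − 0.9×0.96 = 0.136, an apparent effectiveness of 28%. The range is 10% to 71%, again with no effect on transfer.

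**3. Selection in the other direction**

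Suppose a behavioural factor, present in 20% of mothers, multiplies wart risk by 3 to 5 and JoRRP risk by 2 to 3. Suppose also that the vaccine is one third as effective in those mothers (all assumed, ve 0.6 or 0.88). Vaccinated mothers with warts then have the factor more often. The stratum OR, vaccinated versus unvaccinated, is 1.10 to 1.42, which is apparent harm.

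**4. The EGW-no stratum**

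If ve applies to 6/11 infection, wart risk given infection does not depend on vaccination, and infection is uncommon, the OR without EGW is roughly 1/(1−ve). At ve = 0.38 that is 1/0.62 = 1.6, against 1.06 with EGW (s = 0.90). At ve = 0.88 it is 1/0.12 = 8.3, against 1.73. The protocol's expectation for women without EGW is therefore consistent with this model.

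**5. How many cases the stratum would hold**

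With 200 cases, 5% coverage in controls and a protective OR of 1/3, the vaccination odds in cases are (0.05/0.95)/3 = 0.0175, a proportion of 0.0172, or about 3.4 vaccinated cases. If 20% to 80% of these fall in the EGW-yes stratum (assumed), that is about 0.7 to 2.8 cases.

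**The case against.** The strongest defence is that the protocol handles the mediator correctly where it matters. Annex 1 identifies it, Table 3 footnote 3 leaves it out of the adjustment set, the split is a sensitivity analysis, and note 2(d) gives the result regardless of EGW. Blocked transfer is not a study objective and has no success criterion. The wording is conditional and tentative. The stratum will hold very few vaccinated cases, so a convincing effect there is unlikely. Part of the remedy is also in the plan already, since 7.8.2 compares pre-vaccination wart history at the same attained age.

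All of this stands, and it limits the reach of the point. It does not repair the sentence, which is tied to warts before delivery. Sparse data make a chance finding harder to interpret, and 7.8.2 commits to reporting all results.

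Three stronger readings are tempting and should be resisted:
- A reader might infer that the protocol claims proof of blocked transfer. It says only that the result would suggest it.
- A reader might infer that the primary vaccine effect is biased by this split. It is not, because EGW before delivery does not enter that model.
- A reader might infer that the expectation of higher effectiveness without EGW is also wrong, since that stratum leaves out prevention through warts. Removing those women changes absolute risk but not the relative effect on wart-free 6/11 infection. Step 4 gives a larger OR there.

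It is also fair that type mix is only one mechanism, that it is weak at the low end of the effectiveness range, and that step 3 goes the other way. This supports saying that the stratum cannot identify the mechanism. It does not support saying that the stratum is biased in a known direction.

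**Conclusion.** The inference from the EGW-yes stratum to blocked transfer is unsound as stated. With no transfer effect, type mix alone yields an OR of about 1.06 to 1.73. This rests on the section 7.5 range used as type-specific effectiveness, an assumed 90% 6/11 share and no JoRRP from other wart types. Prevented new infection can also mimic protection, and behavioural selection can mask or reverse it. Neither a protective nor a null result in that stratum would speak to transfer.

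It is unclear whether the section 7.8.1 exclusion carries into Table 3 note 2(c). If it does, vaccinated mothers in the stratum have only post-vaccination warts while unvaccinated mothers have warts from any time. If it does not, step 2 applies as well. The conclusion is the same either way.

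The point concerns the interpretation of one sensitivity stratum. It should be corrected, and the primary analysis stands.

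**What to change.** 1. In sections 7.2.3 and 7.8.2 and in Table 3 note 2(c), define the stratum used for interpretation by EGW before vaccination. For unvaccinated mothers, use history up to the same attained age, as 7.8.2 already does for its descriptive comparison. State that the section 7.8.1 exclusion does not apply to this table.
2. Keep the table by EGW before delivery, labelled descriptive.
3. Delete the transfer sentence in 7.8.2, or qualify it by naming type mix, selection of vaccinated mothers with warts, and prevented new infection as rival explanations. The qualification is needed even with the new stratum, because step 2 shows that prevented new infection still competes there.
4. Leave the statement about women without EGW as it is.

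The cost is assigning a reference age to unvaccinated mothers, slightly more analysis work and the loss of one mechanistic interpretation. The change needs no new data source and does not touch the primary estimate.

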### 7.8.3 Exploratory Objectives: Calculation of Epidemiological Measures of Interest

Risk factors for JoRRP will be explored in the VE analysis conditional logistic regression model to evaluate if they are independently statistically significantly associated with the outcome of JoRRP, with all other factors held constant. Specifically, vaccination exposure will be at the reference level (i.e., unvaccinated).

Information will be presented on biological mother-child pairs, focusing on concordant and discordant pairs for JoRRP and AoRRP (history of diagnosis, identified using ICD-10 code D14.1), e.g., preparation of summary 2x2 table (if possible). Due to strict data protection regulation in Europe, it is not possible to include exact counts if <5 in an individual cell.

## 7.9 Quality Control

By signing this protocol, all parties agree to following applicable standard operating procedures (SOPs). All parties also agree to ensuring all existing and new study personnel are appropriately trained to ensure the study is conducted and data are generated, documented, and reported in compliance with the protocol, Good Pharmacoepidemiology Practice (GPP), Good Pharmacovigilance Practices (GVP), and all applicable federal, state, and local laws, rules and regulations. All parties should maintain transparency and open communication in order to effectively manage the study and proactively mitigate any risks.

The Sponsor may conduct routine or for-cause audits to ensure oversight and conduct of the study are completed in accordance with the protocol, quality standards (e.g., GPP and GVP), and applicable laws and regulations. If a significant quality issue (SQI) is identified at any time during the conduct of the study, it must be escalated to the Sponsor immediately. A SQI is any issue with the potential to negatively impact, either directly or indirectly, the rights, safety and well-being of patients or study participants and/or the integrity of the data. In the event an audit or SQI results in corrective or preventive actions, all parties are expected to appropriately implement the action plan in a timely manner.

## 7.10 Limitations of the Research Methods

This is a register-based study which relies on the use of a proxy codes rather than medical records. It is thus limited in terms of density of data, such that there is not access to all medical details for each case. On the other hand, there is excellent systematicity, and generalizability due to the structural nature of the register sampling frame. There is also no available explicit information on certain lifestyle factors of the mother, such as sexual behavior; however, there are several proxy variables that may serve to adjust for potential confounding (Annex 1). Additionally, with use of registry data from three different countries, some variables may need to be adapted to be able to combine information as it is not identical in all registers. This will be achieved via development of a common data model, involving collaboration between all Nordic country investigators.

Given that the main cause of JoRRP globally is infection with HPV type 6 or 11, results are expected to be generalizable. With the proposed study population design, there is restriction

PRODUCT: V501/V503	PROTOCOL/AMENDMENT VERSION NO.: V503-095-00-v3
REVOPS ID NO: NIS102781	CORE DRC APPROVAL DATE: 18MAR2024
EPIDEMIOLOGY NO.(PE STUDIES ONLY): 08039.022	

in analytical format; as having access to the full baseline cohort will yield many technical advantages. The risk for misclassification of exposure to vaccination is minimized through substantial knowledge and experience utilizing vaccination registries by investigators in each of the respective countries. Nonetheless there is a small but existing risk of non-differential misclassification of the outcome. Generalizability is maximized through the population-based sampling frame and allowing all eligible study participants who are alive and reside in Sweden, Denmark, and Norway at the appropriate time to enter. Also, in recent years, especially the post-vaccination introduction era, Sweden, Denmark, and Norway have experienced high immigration, which may further increase generalizability of study results.

### 7.11 Methods to Minimize Bias

A register-based proxy for definition of outcome (JoRRP) will be used, i.e., ICD-10 code D14.1, which in all countries (Sweden, Denmark, and Norway) is used to register the disease category “benign tumor of the larynx”. Where possible, appropriate topography/morphology codes for RRP will also be applied to further increase outcome specificity. Additionally, in sensitivity analyses, diagnostic and treatment codes described above will be applied to also improve specificity in settings where topography/morphology codes cannot be accessed in the pathology or cancer registry. Given that granulomas of the larynx are largely occurring in middle-age, male smokers, it is suggested that benign tumors of the larynx, other than HPV-associated papilloma, among children (ages 0-9 years), will be very rare. If a misclassification of outcome due to using D14.1 would sometimes occur, it will likely lead to bias towards the null, which means that if vaccine effectiveness against JoRRP is observed, the true effect is likely greater.

Given the rarity of JoRRP, and the strong registration of Swedish, Danish, and Norwegian healthcare, it is believed that virtually all cases of JoRRP will be identified by the above algorithm. The risk that a control selected at random from the underlying population is actually a false negative, i.e., a missed case of RRP, should be negligible.

All subjects whose mother immigrated to Sweden, Denmark, or Norway (after age 9) will be excluded, to ensure there is no misclassification of exposure, which removes the risk that mothers who have received HPV vaccination outside of their country are mis-classified as non-vaccinated. Also, to ensure that prevalent cases of JoRRP are excluded, subjects (children) born or ever living in another country will not be eligible, as follow-up in registries may be insufficient to determine if incident case is truly new onset.

Furthermore, adjustment for potential confounders will be employed in the conditional logistic regression model, for factors that are shown to be associated with both exposure and outcome (see Annex 1 for details). The spectrum of confounding factors can be determined both *a priori*/empirically, through subject matter knowledge and literature review, but also (once data on potential confounders are collected) by investigation of variables in the regression model, whereby covariates are examined in terms of whether their removal from the model substantially (e.g., by  $\geq 10\%$ ) alters the width of the confidence interval for the observed (odds ratio) association between exposure and outcome in the actual model.

PRODUCT: V501/V503	PROTOCOL/AMENDMENT VERSION NO.: V503-095-00-v3
REVOPS ID NO: NIS102781	CORE DRC APPROVAL DATE: 18MAR2024
EPIDEMIOLOGY NO.(PE STUDIES ONLY): 08039.022	

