## 3. Pregnancy delivery method

There have been no studies showing an association between method of delivery (vaginal versus cesarean section) and willingness to vaccinate against HPV in Nordic region or elsewhere. An association between method of delivery and HPV vaccination can therefore be questioned.

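### Section 7.11 judges candidate confounders by a change in confidence interval width, but confounding shows as a change in the odds ratio

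*Protocol*

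**What the plan says.** Section 7.11 offers two routes to the set of confounders. One is a priori, "through subject matter knowledge and literature review". The other is empirical, "by investigation of variables in the regression model, whereby covariates are examined in terms of whether their removal from the model substantially", with 10% or more given as an example, "alters the width of the confidence interval for the observed (odds ratio) association between exposure and outcome in the actual model". No rule based on change in the odds ratio appears anywhere in the protocol. Annex 1 defines a confounder as a factor associated with both exposure and outcome, so that the observed association between them is distorted.

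The status of each covariate differs by place:

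- **Income and education.** Section 7.8.2 is firm. Its list opens "Potential confounders such as mode of delivery, as well highest level of family income and education achieved by the mother" and states that these "will be adjusted for when investigating the primary objective, through inclusion in the conditional logistic regression". Annex 1 is also firm. Table 3, footnote 3, lists them only as candidates.
- **Mode of delivery.** Firm in Section 7.8.2, to be explored in the Annex 1 conclusions, and a candidate in Table 3. On its link with vaccination, Annex 1 says: "An association between method of delivery and HPV vaccination can therefore be questioned".
- **Smoking.** Not named in the adjustment sentence of Section 7.8.2. The Annex 1 conclusions say "the analysis will include adjustment for income, education and smoking as a proxy for sexual behavior", then in a later paragraph that smoking will be explored. It is a candidate in Table 3.
- **Mother's country of birth.** Not named in that sentence of Section 7.8.2, planned for inclusion in the Annex 1 conclusions, and a candidate in Table 3.

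**The concern.** A covariate confounds when leaving it out moves the estimated odds ratio. Interval width on the log scale depends on the standard error, which here is set almost entirely by the small number of cases with a vaccinated mother. A test on width can therefore pass over a covariate that shifts the estimate. It can also retain one that only changes precision.

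This matters because the adjusted odds ratio in Table 3 is the main result, and Section 7.5 sets fixed success thresholds (odds ratio at least 3.0, lower limit at least 1.33). Where the sections disagree on whether a covariate is in the model, the empirical rule is what remains to decide it, after the data have been seen.

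**Working it through.** The protocol attaches no calculated figure to this rule, only the 10% example, so there is nothing to reproduce. The check asks how width and odds ratio respond when a covariate Z is removed.

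**Inputs.** From the protocol: 200 cases and 20,000 controls; true odds ratio 3.0, unvaccinated versus fully vaccinated (the direction of Table 3); 5% coverage, the low end in Section 7.5; uptake ratio 0.32 for Z (Annex 1, low education, Swedish subsidized programme). Assumed: Z present in 30% of mothers; outcome risk ratio 3 for Z. Matching is ignored.

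**Formulas.** Log-scale width = 2 × 1.96 × SE. Odds-ratio-scale width = OR × (exp(1.96 SE) − exp(−1.96 SE)) = 2 × OR × sinh(1.96 SE).

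**Step 1: a strong confounder.**
- Coverage without Z: 0.05 / (0.7 + 0.3 × 0.32) = 0.0628. With Z: 0.32 × 0.0628 = 0.0201.
- Controls: 1,000 vaccinated, 19,000 unvaccinated. Expected cases: 2.655 vaccinated, 197.345 unvaccinated.
- Z omitted: OR = (197.345 / 2.655) / (19,000 / 1,000) = 3.91; SE = √(1/2.655 + 1/197.345 + 1/1,000 + 1/19,000) = 0.619. The first term is 0.377 of a total of 0.383, so vaccinated cases fix the precision.
- Z included (logistic model on the expected counts): OR 3.00, SE 0.620.
- On removal: odds ratio +30%; log-scale width −0.3%; odds-ratio-scale width 9.23 to 11.99, +30%.

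A 10% rule on log-scale width misses this covariate. The same rule on the odds ratio scale keeps it.

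**Step 2: a wider grid.** There were 48 settings: true OR 2 or 3, coverage 5% or 10%, odds ratio of Z with vaccination 0.1 to 20, and of Z with JoRRP 1 to 3. Wherever Z confounded, removal moved the odds ratio by 10% to 72%. Log-scale width never changed by more than 6.8%, so a 10% rule on that scale never flagged a confounder. Odds-ratio-scale width stayed within about 5 percentage points of the change in the odds ratio.

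One setting resembles country of birth: uptake odds ratio 0.49 (Annex 1), with prevalence 15% and outcome odds ratio 3 both assumed. At 5% coverage the odds ratio goes from 3.00 to 3.37 (+12.4%), log-scale width changes by −0.1%, and odds-ratio-scale width by +12.2%.

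**Step 3: precision alone, odds ratio scale.** With no confounding, expected vaccinated cases are 200 × 0.05 / (0.05 + 3 × 0.95) = 3.45, giving SE 0.544. Take SE 0.543 without a covariate and 0.584 with it (+7.5%), the odds ratio unchanged. The sinh terms are 1.277 and 1.411. Adding the covariate changes width by 1.411/1.277 − 1 = +10.5%; removing it changes width by 1.277/1.411 − 1 = −9.5%. A full 10% fall on removal needs an SE of about 0.586, a rise of 8%.

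**Step 4: offset, odds ratio scale.** Assumed values: crude OR 3.0 (SE 0.55), adjusted OR 2.6 (SE 0.60). The odds ratio changes by 3.0/2.6 − 1 = 15%, the width by only 2%. A confounder is missed because the two movements cancel.

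**The case against.** The strongest reply is that Section 7.11 refers to the interval for the odds ratio, and on that scale width is proportional to the estimate, so the rule mostly behaves like a change-in-estimate rule. That stands for the modelled settings. The failures in Steps 3 and 4 need SE inflation of about 7.5% to 9%, whereas the largest in the grid was about 7%. The reply does not rescue the wording: the scale is not stated, and the verdict on the same covariate can reverse with it.

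A second reply is that the empirical step is permissive, sits beside a priori selection, and gives 10% only as an example. This stands and limits the consequence.

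Two stronger readings are tempting and are not supported:

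- **That the rule drops socioeconomic status.** Section 7.8.2 and Annex 1 both commit to income and education; only the Table 3 footnote is tentative. The numbers do not carry it either. Pairing 0.32 with 3.21/1.98 = 1.62 at 30% prevalence gives odds ratio +10.9% and odds-ratio-scale width +10.6%, so on that scale the rule keeps the covariate. The pair is also mismatched: 0.32 is the most extreme education estimate in Annex 1, and 1.62 compares US public with private insurance. With the school-programme education estimates (0.75 to 0.92) the odds ratio moves only about 1% to 3%.
- **That mode of delivery must come out of the model.** Annex 1 questions its link with vaccination, but says the same of smoking and cites a risk ratio of 1.00 for smoking with JoRRP. The documents support reconciling its status; they do not settle which status is right.

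**Conclusion.** The point holds as a defect in a stated criterion. On the log scale, a 10% width rule flagged none of the confounders modelled, including one that moved the odds ratio by 30%. On the odds ratio scale it usually gives the right answer, but it can be triggered or cancelled by precision.

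The practical exposure is limited to smoking, mother's country of birth and mode of delivery, the covariates that the sections leave open. The size of any resulting bias cannot be stated from the protocol: the 30% and 12.4% figures rest on assumed prevalences and outcome associations, and for smoking and mode of delivery Annex 1 reports no established link with vaccination. The correction should be made before the analysis because it concerns the primary model. It does not show that the primary result would be wrong.

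**What to change.** In Section 7.11, replace the reference to interval width with a change of 10% or more in the odds ratio estimate on removal of the covariate, or delete the empirical step. Then state one a priori primary adjustment set, in the same terms, in Section 7.8.2, the Annex 1 conclusions and Table 3 footnote 3. Give mode of delivery, smoking and mother's country of birth each a single status: in the primary model, or exploratory only.

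The cost is wording. All five covariates are already listed in Section 7.3.3, so no new data are needed. A fixed set may cost a little precision if it includes a covariate that turns out not to confound.
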